#### 1.1.3 Exploratory Objectives

- To evaluate the concordance (or discordance) of TROP2 expression between archival tissues and pretreatment fresh biopsies
- To identify baseline characteristics of gene expressions of DNA repair pathways in participants with or without clinical response
- To identify mutations of TROP2 gene (*TACSTD2*) in tumors with resistance against SG
- To investigate systemic pharmacodynamic biomarkers before and after SG treatment (i.e., circulating tumor DNA [ctDNA], circulating tumor cells [CTC], and  $\gamma$ H2AX expression)
- To evaluate *UGT1A1*\*28 allele as a predictive marker for gastrointestinal and hematologic toxicities

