### **6 DATA COLLECTION AND EVALUATION**

#### **6.1 DATA COLLECTION**

The PI will be responsible for overseeing entry of data into a 21 CFR Part 11-compliant data capture system provided by the NCI CCR and ensuring data accuracy, consistency and timeliness. Principal Investigator, associate investigators/research nurses and/or a contracted data manager will assist with the data management efforts. Primary and final analyzed data will have identifiers so that research data can be attributed to an individual human subject participant.

All adverse events (AEs), including clinically significant abnormal findings on laboratory evaluations, regardless of severity, will be followed until return to baseline or stabilization of event.

Document AEs from the first study intervention, Study Day 1 through 30 days after the subject received the last product administration. Beyond 30 days after the last intervention, only adverse events which are serious and related to the study intervention need to be recorded.

An abnormal laboratory value will be recorded in the database as an AE only if the laboratory abnormality is characterized by any of the following:

- Results in discontinuation from the study
- Is associated with clinical signs or symptoms
- Requires treatment or any other therapeutic intervention
- Is associated with death or another serious adverse event, including hospitalization.
- Is judged by the Investigator to be of significant clinical impact
- If any abnormal laboratory result is considered clinically significant, the investigator will provide details about the action taken with respect to the test drug and about the participant's outcome.

The PI (or designee) evaluation of each AE not captured in the clinical database determining that it meets the criteria above will be documented in the source documents. Note: the investigator

performing the assessment must be a clinician licensed to diagnose and listed on the FDA Form 1572.

**End of study procedures:** Data will be stored according to HHS, FDA regulations, and NIH Intramural Records Retention Schedule as applicable.

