### **10.5.3 Analysis of the Secondary Endpoints**

#### **10.5.3.1 Safety**

Safety will be reported by describing AE per CTCAE v5.0, by type and grade of toxicity, as detailed in Section [6.3](#).

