#### **10.5.4 Safety Analyses**

To assess safety in previously treated ovarian, endometrial, and cervical cancer participants, the toxicity grade and type will be reported for all participants treated in the three cohorts or separately by cohort.

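### Laboratory values become AEs without regard to CTCAE grade and no graded laboratory table is planned, so some asymptomatic grade 3-4 cytopenias can be missing from the safety results

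*Combined protocol and SAP*

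**What the plan says.** Section 6.1 states the recording rule: "An abnormal laboratory value will be recorded in the database as an AE only if the laboratory abnormality is characterized by" at least one of five features. These are discontinuation from the study; clinical signs or symptoms; "Requires treatment or any other therapeutic intervention"; "Is associated with death or another serious adverse event, including hospitalization"; and "Is judged by the Investigator to be of significant clinical impact". None refers to CTCAE grade, and none names a dose hold, delay or reduction.

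The safety output is built on AEs. Section 10.5.3.1: "Safety will be reported by describing AE per CTCAE v5.0, by type and grade of toxicity". Section 10.5.4: "the toxicity grade and type will be reported for all participants treated in the three cohorts or separately by cohort". No section plans a table of graded laboratory values. Section 10.5.3.1 refers the reader to Section 6.3 for detail, but that section holds the tumor response criteria; the toxicity criteria are in 6.4.

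The Study Calendar (3.4) schedules a CBC with differential at screening, at baseline, on Days 1 and 8 of every cycle, and at end of treatment. Section 6.4 makes CTCAE v5.0 the grading standard. Section 8.1.1 defines an AE so as to include abnormal laboratory findings, without the gate in 6.1.

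An exploratory objective (1.1.3) is to evaluate the UGT1A1*28 "allele as a predictive marker for gastrointestinal and hematologic toxicities". Sections 5.2.1, 10.1 and 10.5.8 do not say whether hematologic toxicity is to be taken from AE records or from CBC values.

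**The concern.** A laboratory grade is an objective measurement that the trial already makes at fixed times. Under Section 6.1, whether that measurement reaches the safety tables can depend on whether someone treated it or thought it important. Two participants with the same nadir may then be counted differently. Since the rule can only remove events, the reported cytopenia rates could be too low, by an amount nobody could later read from the AE tables.

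This matters most for hematologic toxicity, a leading toxicity of SG and one of the two outcomes named in the UGT1A1 objective. The primary endpoint and the two-stage decision rule are not touched.

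**Working it through.** **1. The protocol's own figure.** Section 1.2.4.2 gives grade 3 or higher neutropenia as 34.5%. Table 1: (65 + 24)/258 = 89/258 = 34.5%, which reproduces. Table 1 lists neutrophil count decreased as a separate term: (32 + 22)/258 = 54/258 = 20.9%. The overlap is not given, so the share with either term lies between 34.5% (the second wholly inside the first) and (89 + 54)/258 = 55.4% (no overlap). The rate of low counts thus already depends on how they are recorded.

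**2. Which events pass the gate.** Setting Section 6.1 beside Table 2 and Section 4.2:
- *Neutropenia that delays a dose and receives G-CSF.* Table 2 pairs this event with G-CSF, and Section 4.2.2 recommends it for managing neutropenia. The treatment criterion is met, so it is captured.
- *Neutropenia without G-CSF.* Table 2 gives G-CSF when clinically indicated, and a grade 4 count lasting under 7 days need not trigger the row. If asymptomatic, it enters by judgement only.
- *Low counts at end of treatment.* There is no next dose to delay. If untreated and asymptomatic, judgement only.
- *Other cytopenias.* Table 2's row for nonneutropenic hematologic toxicity calls for delay and dose reduction, with no treatment. Untransfused anemia, thrombocytopenia or leukopenia without symptoms enters by judgement only. Transfused anemia (4.2.3) is captured.
- *Stopping SG.* The criterion is discontinuation from the study. Sections 3.6.1 and 3.6.2 keep that separate from leaving therapy.

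**3. How much rests on the treatment and judgement criteria.** From Table 4, heterozygous plus wild type:
- grade 3-4 neutropenia: (204 + 180)/(420 + 416) = 384/836 = 45.9%
- grade 3-4 febrile neutropenia: (22 + 23)/836 = 45/836 = 5.4%

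Taking febrile cases as a subset (assumption), (384 - 45)/384 = 339/384 = 88% were not febrile. These are not all lost; many would pass through G-CSF or another criterion.

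**4. Range for the recorded rate.** Take the Table 4 rates as true, and let c be the fraction of non-febrile cases that pass the gate. The recorded rate is (45 + 339c)/836:

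| c (assumed) | Recorded rate | Of 66 participants |
|---|---|---|
| 0 | 5.4% | 3.6 |
| 0.25 | 15.5% | 10.2 |
| 0.50 | 25.7% | 16.9 |
| 0.75 | 35.8% | 23.6 |
| 1 | 45.9% | 30.3 |

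The row c = 0 is an extreme bound, not a forecast. The documents do not give c.

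**5. Effect on the UGT1A1 contrast.** Heterozygous minus wild type: 204/420 - 180/416 = 48.6% - 43.3% = 5.3 points. If 80% or 60% of all events are recorded equally in both groups (assumption), the gap is 0.8 × 5.3 = 4.2 or 0.6 × 5.3 = 3.2 points. Under the model in step 4 it is 26.9% - 24.4% = 2.5 points at c = 0.5 and 5.2% - 5.5% = -0.3 at c = 0. With 33 participants per genotype group (66/2, assumption), the standard error of the difference is √[(0.486 × 0.514 + 0.433 × 0.567)/33] = 0.12, or 12 points. Even the extreme shift, from 5.3 to -0.3, is less than half of one standard error.

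**The case against.** The strongest reply is that the protocol's own management rules bring most of the important events back in. On-treatment CBCs fall on dosing days, Section 3.2 gives ANC thresholds for withholding on those days, and Table 2 attaches G-CSF to neutropenia that delays a dose. Such an event will often meet the treatment criterion. In addition, the team discusses each patient weekly and the PI reviews AE data (7.3.1), and the clinical-impact criterion lets an investigator record any value. All of this stands and narrows the gap. It does not close it: G-CSF is conditional, the nonneutropenic row of Table 2 carries no treatment, end-of-treatment values have no dosing consequence, and review by judgement is what a graded table would supplement.

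Some stronger readings are tempting but not supported:
- *Dose-delaying neutropenia in general goes unrecorded.* Table 2 points the other way wherever G-CSF is given.
- *The trial's rates will not be comparable with Table 4.* Table 4 is headed as adverse reactions, and Table 1 reports treatment-emergent AEs. Nothing shows that either came from laboratory values, so AE-based rates may be the closer match.
- *The genotype gap at risk is the homozygous versus wild-type one,* 58.0% - 43.3% = 14.8 points before rounding. Section 2.1.2.9 excludes known homozygotes. Untested ones could enter, but few are likely: 46 of the 403 genotyped patients in the earlier basket study (1.2.5), or 11%.
- *The UGT1A1 analysis will use the filtered AE records.* The source is unspecified, so CBC values are not ruled out.

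**Conclusion.** The gap is real and of moderate importance. Followed as written, the plan allows asymptomatic, untreated grade 3-4 cytopenias measured on scheduled CBCs to be missing from the safety tables, and no other planned output would show them. It applies mainly to neutropenia without G-CSF, end-of-treatment values, and thrombocytopenia, leukopenia or anemia handled only by delay or dose reduction.

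The number of events lost cannot be derived from the documents. The range in step 4 rests on assumed capture fractions, on Table 4 rates applying here, and on febrile cases being a subset.

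For UGT1A1 the defect is that the outcome source is not named. The effect on this descriptive analysis is small beside its sampling error, provided capture is similar in both genotype groups. Section 10.1 says that genotype may guide toxicity management in this study, so capture could differ by genotype; the documents do not allow that to be sized.

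**What to change.** Add to Section 10.5.3.1: the worst on-study CTCAE v5.0 grade per participant for neutrophils, hemoglobin, platelets and WBC will be derived from all CBC values, scheduled or not, and tabulated by cohort beside the AE tables. State the window; first dose to 30 days after the last dose would match AE collection in 6.1.

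In Section 5.2.1 or 10.5.8, name this worst grade as the hematologic outcome for the UGT1A1 analysis, and show AE-based rates as well for comparison with Tables 1 and 4.

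Reconcile the recording rule in 6.1 with the AE definition in 8.1.1, for example by stating that 8.1.1 is the general definition and 6.1 governs database entry. Correct the reference in 10.5.3.1 from Section 6.3 to 6.4. The recording rule itself can stay.

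The cost is a little programming on measurements already scheduled, plus a data extract if CBC results are not held in the trial database, which the documents do not say. Reported cytopenia rates may look higher. Laboratory grades remove the dependence on recording judgement, but not the effect of G-CSF or transfusion on the counts themselves.

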## 6.2 PUBLICATION AND DATA SHARING POLICY

### 6.2.1 NIH Data Management and Sharing Policy and NIH Genomic Data Sharing Policy Compliance

This study will comply with the NIH Data Management and Sharing (DMS) Policy, which applies to all new and ongoing NIH-funded research in the IRP, as of January 25, 2023, that is associated with a ZIA, with a clinical protocol that undergoes scientific review and/or will involve genomic data sharing.

This study will comply with the NIH Genomic Data Sharing (GDS) Policy, which applies to all new and ongoing NIH IRP-funded research, as of January 25, 2015, that generates large-scale human or non-human genomic data, as well as the use of these data for subsequent research. Large-scale data include genome-wide association studies (GWAS), single nucleotide polymorphisms (SNP) arrays, and genome sequence, transcriptomic, epigenomic, and gene expression data.

Therefore, unlinked genomic data will be deposited in public genomic databases such as dbGaP in compliance with the NIH Genomic Data Sharing Policy.

### 6.2.2 NIH Public Access Policy Compliance

This study will comply with the NIH Public Access Policy, which ensures that the public has access to the published results of NIH funded research. It requires scientists to submit final peer-reviewed journal manuscripts that arise from NIH funds to the digital archive PubMed Central upon acceptance for publication.

## 6.3 RESPONSE CRITERIA

For the purposes of this study, participants should be re-evaluated for response as noted in Section 3.1. In addition to a baseline scan, confirmatory scans should also be obtained within 8 weeks (not less than 4 weeks) following initial documentation of objective response.

Response and progression will be evaluated in this study using the new international criteria proposed by the revised Response Evaluation Criteria in Solid Tumors (RECIST) guideline (version 1.1) [101]. Changes in the largest diameter (unidimensional measurement) of the tumor lesions and the shortest diameter in the case of malignant lymph nodes are used in the RECIST criteria.

### 6.3.1 Disease Parameters

Measurable disease: Measurable lesions are defined as those that can be accurately measured in at least one dimension (longest diameter to be recorded) as:

- By chest x-ray:  $\geq 20$  mm;
- By CT scan:
  - Scan slice thickness 5 mm or under: as  $\geq 10$  mm
  - Scan slice thickness  $>5$  mm: double the slice thickness

- With calipers on clinical exam:  $\geq 10$  mm.

All tumor measurements must be recorded in millimeters (or decimal fractions of centimeters).

**Malignant lymph nodes.** To be considered pathologically enlarged and measurable, a lymph node must be  $\geq 15$  mm in short axis when assessed by CT scan (CT scan slice thickness recommended to be no greater than 5 mm). At baseline and in follow-up, only the short axis will be measured and followed.

**Non-measurable disease.** All other lesions (or sites of disease), including small lesions (longest diameter  $<10$  mm or pathological lymph nodes with  $\geq 10$  to  $<15$  mm short axis), are considered non-measurable disease. Bone lesions, leptomeningeal disease, ascites, pleural/pericardial effusions, lymphangitis cutis/pulmonitis, inflammatory breast disease, and abdominal masses (not followed by CT or MRI), are considered as non-measurable.

Note: Cystic lesions that meet the criteria for radiographically defined simple cysts should not be considered as malignant lesions (neither measurable nor non-measurable) since they are, by definition, simple cysts.

‘Cystic lesions’ thought to represent cystic metastases can be considered as measurable lesions, if they meet the definition of measurability described above. However, if non-cystic lesions are present in the same participant, these are preferred for selection as target lesions.

**Target lesions.** All measurable lesions up to a maximum of 2 lesions per organ and 5 lesions in total, representative of all involved organs, should be identified as **target lesions** and recorded and measured at baseline. Target lesions should be selected on the basis of their size (lesions with the longest diameter), be representative of all involved organs, but in addition should be those that lend themselves to reproducible repeated measurements. It may be the case that, on occasion, the largest lesion does not lend itself to reproducible measurement in which circumstance the next largest lesion which can be measured reproducibly should be selected. A sum of the diameters (longest for non-nodal lesions, short axis for nodal lesions) for all target lesions will be calculated and reported as the baseline sum diameters. If lymph nodes are to be included in the sum, then only the short axis is added into the sum. The baseline sum diameters will be used as reference to further characterize any objective tumor regression in the measurable dimension of the disease.

**Non-target lesions.** All other lesions (or sites of disease) including any measurable lesions over and above the 5 target lesions should be identified as **non-target lesions** and should also be recorded at baseline. Measurements of these lesions are not required, but the presence, absence, or in rare cases unequivocal progression of each should be noted throughout follow-up.

### 6.3.2 Methods for Evaluation of Measurable Disease

All measurements should be taken and recorded in metric notation using a ruler or calipers. All baseline evaluations should be performed as closely as possible to the beginning of treatment and never more than 4 weeks before the beginning of the treatment.

The same method of assessment and the same technique should be used to characterize each identified and reported lesion at baseline and during follow-up. Imaging-based evaluation is preferred to evaluation by clinical examination unless the lesion(s) being followed cannot be imaged but are assessable by clinical exam.

Clinical lesions: Clinical lesions will only be considered measurable when they are superficial (e.g., skin nodules and palpable lymph nodes) and  $\geq 10$  mm diameter as assessed using calipers (e.g., skin nodules). In the case of skin lesions, documentation by color photography, including a ruler to estimate the size of the lesion, is recommended.

Chest x-ray: Lesions on chest x-ray are acceptable as measurable lesions when they are clearly defined and surrounded by aerated lung. However, CT is preferable.

Conventional CT and MRI: This guideline has defined measurability of lesions on CT scan based on the assumption that CT slice thickness is 5 mm or less. If CT scans have slice thickness greater than 5 mm, the minimum size for a measurable lesion should be twice the slice thickness. MRI is also acceptable in certain situations (e.g. for body scans).

Use of MRI remains a complex issue. MRI has excellent contrast, spatial, and temporal resolution; however, there are many image acquisition variables involved in MRI, which greatly impact image quality, lesion conspicuity, and measurement. Furthermore, the availability of MRI is variable globally. As with CT, if an MRI is performed, the technical specifications of the scanning sequences used should be optimized for the evaluation of the type and site of disease. Furthermore, as with CT, the modality used at follow-up should be the same as was used at baseline and the lesions should be measured/assessed on the same pulse sequence. It is beyond the scope of the RECIST guidelines to prescribe specific MRI pulse sequence parameters for all scanners, body parts, and diseases. Ideally, the same type of scanner should be used and the image acquisition protocol should be followed as closely as possible to prior scans. Body scans should be performed with breath-hold scanning techniques, if possible.

PET-CT: At present, the low dose or attenuation correction CT portion of a combined PET-CT is not always of optimal diagnostic CT quality for use with RECIST measurements. However, if the site can document that the CT performed as part of a PET-CT is of identical diagnostic quality to a diagnostic CT (with IV and oral contrast), then the CT portion of the PET-CT can be used for RECIST measurements and can be used interchangeably with conventional CT in accurately measuring cancer lesions over time. Note, however, that the PET portion of the CT introduces additional data which may bias an investigator if it is not routinely or serially performed.

Ultrasound: Ultrasound is not useful in assessment of lesion size and should not be used as a method of measurement. Ultrasound examinations cannot be reproduced in their entirety for independent review at a later date and, because they are operator dependent, it cannot be guaranteed that the same technique and measurements will be taken from one assessment to the next. If new lesions are identified by ultrasound in the course of the study, confirmation by CT or MRI is advised. If there is concern about radiation exposure at CT, MRI may be used instead of CT in selected instances.

Endoscopy, Laparoscopy: The utilization of these techniques for objective tumor evaluation is not advised. However, such techniques may be useful to confirm complete pathological response when biopsies are obtained or to determine relapse in trials where recurrence following complete response (CR) or surgical resection is an endpoint.

Tumor markers: Tumor markers alone cannot be used to assess response. If markers are initially above the upper normal limit, they must normalize for a participant to be considered in complete clinical response. Specific guidelines for both CA-125 response (in recurrent ovarian cancer) and PSA response (in recurrent prostate cancer) have been published[[102](#), [103](#)]. In addition, the

Gynecologic Cancer Intergroup has developed CA-125 progression criteria which are to be integrated with objective tumor assessment for use in first-line trials in ovarian cancer [104].

Cytology, Histology: These techniques can be used to differentiate between partial responses (PR) and complete responses (CR) in rare cases (e.g., residual lesions in tumor types, such as germ cell tumors, where known residual benign tumors can remain).

The cytological confirmation of the neoplastic origin of any effusion that appears or worsens during treatment when the measurable tumor has met criteria for response or stable disease is mandatory to differentiate between response or stable disease (an effusion may be a side effect of the treatment) and progressive disease.

FDG-PET: While FDG-PET response assessments need additional study, it is sometimes reasonable to incorporate the use of FDG-PET scanning to complement CT scanning in assessment of progression (particularly possible 'new' disease). New lesions on the basis of FDG-PET imaging can be identified according to the following algorithm:

- a. Negative FDG-PET at baseline, with a positive FDG-PET at follow-up is a sign of PD based on a new lesion.
- b. No FDG-PET at baseline and a positive FDG-PET at follow-up: If the positive FDG-PET at follow-up corresponds to a new site of disease confirmed by CT, this is PD. If the positive FDG-PET at follow-up is not confirmed as a new site of disease on CT, additional follow-up CT scans are needed to determine if there is truly progression occurring at that site (if so, the date of PD will be the date of the initial abnormal FDG-PET scan). If the positive FDG-PET at follow-up corresponds to a pre-existing site of disease on CT that is not progressing on the basis of the anatomic images, this is not PD.
- c. FDG-PET may be used to upgrade a response to a CR in a manner similar to a biopsy in cases where a residual radiographic abnormality is thought to represent fibrosis or scarring. The use of FDG-PET in this circumstance should be prospectively described in the protocol and supported by disease-specific medical literature for the indication. However, it must be acknowledged that both approaches may lead to false positive CR due to limitations of FDG-PET and biopsy resolution/sensitivity.

Note: A 'positive' FDG-PET scan lesion means one which is FDG avid with an uptake greater than twice that of the surrounding tissue on the attenuation corrected image.

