### 3.3 ON STUDY ASSESSMENTS/EVALUATIONS

#### 3.3.1 Timing of Procedures

The following describes all tests and procedures to be conducted during treatment.

Refer to Study Calendar (Section 3.4) for timing and applicable windows.

For each time period, consider the following order of assessments:

- **Screening:** Refer to Section 2.3.
- **Baseline/Cycle 1 Day 1:** The results of all assessments must be available and reviewed prior to initiation of the study drug administration to ensure results still meet standards defined in eligibility criteria. All subjects are required to complete baseline evaluations per the Study Calendar (Section 3.4) within 10 days prior to the first planned dosing of the study drugs, except for imaging tests that are required to be done within 14 (+3) days prior to treatment initiation. Any screening tests performed within the specified time frame for baseline do not need to be repeated.
- **Subsequent Cycles:**
  - Each cycle is 21 days. Beginning with Cycle 2, a permitted range of  $\pm 7$  days due to scheduling or logistical reasons is permitted; however, day 1 of SG in a new cycle may be dosed no less than 14 days from the previous dose of SG (Day 8; [i.e., the Day 8 infusion will be counted as the first day of that 14-day period]). The Day 8 dose of SG may be given no earlier than 6 days from the Day 1 dose (-1/+2 days). The scheduled Day 1 and Day 8 infusions may be delayed for up to 3 weeks for treatment-related toxicities.
  - Pre-Day 1 of each cycle assessment may be done up to 4 days (-4) prior to the start of the cycle.
  - The results of all assessments must be available and reviewed prior to initiation of study drug administration in a new cycle to confirm safety and eligibility for ongoing treatment administration. Components of these panels that are specifically relevant to monitoring the effects of the study drug are specified in “Laboratory Assessment” later in this section. The remaining laboratory values collected on these panels are part of standard of care assessments and unrelated to research. The cycle should be delayed if these criteria are not met (refer to Dose Modifications, Section 3.2.1).

- **Study Drug Administration:**
  - SG will be administered IV on D1 and D8 of 21-day cycles.

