### 3.3.2 Description of Procedures

The following is a description of all procedures:

- Symptom assessment: verbal review of participant's current symptoms to establish a baseline.
- Physical exam, including height, and weight: review of organ systems, weight (kg), height (at screening only) to determine eligibility and establish a baseline.
- Vital signs (i.e., temperature, blood pressure, heart rate and respiratory rate) performed at screening to determine eligibility and establish a baseline, and before, during and after each SG administration to monitor safety.
- Documentation of BRCA mutation (Cohort 1 only) from any certified lab to assess eligibility
- Documentation of and MMR status (Cohort 2 only) and HPV infection status (Cohort 3 only) from any certified lab to establish a baseline.
- Performance status (ECOG): an assessment of activities of daily living; see [Appendix A: Performance Status Criteria](#) to assess eligibility, and to assess response to therapy at subsequent timepoints.
- Laboratory assessments: the following comprises the required tests/analytes to assess eligibility at the time of screening, determination of baseline and treatment continuation per Section [3.2.1](#), and/or the safety of the study drug at subsequent timepoints unless otherwise noted. Additional laboratories may be ordered as part of panels (e.g., acute care panel, comprehensive chemistry, etc.). Given that the methodologies utilized are similar across all laboratories, no significant variability is expected and there is no anticipation that study data will be affected.
  - CBC with differential
  - Serum Chemistries:
    - Acute care panel includes Sodium (Na), Potassium (K), Chloride (Cl) Total CO2 (Bicarbonate), Creatinine, Glucose, Urea nitrogen
    - Hepatic panel includes alkaline phosphatase (AP), ALT, AST, Total Bilirubin, Direct Bilirubin
    - Mineral panel includes Albumin, Calcium, Magnesium, Phosphorus
  - PT/INR and aPTT
  - CA125 (Cohorts 1 and 2 only)
  - Ionized calcium, amylase, lipase
  - Lactate dehydrogenase (LDH)
  - Viral screen: HBsAg, HIV and HCV antibody,
  - CD4 count and HIV VL if HIV positive; HCV viral load if HCV antibody positive
  - HPV DNA testing (Cohort 3 cervical cancer patients only)

- Urinalysis
- Pregnancy test (serum or urine  $\beta$ -hCG) in IOCBP
- Other evaluations:
  - Electrocardiogram (EKG) to determine eligibility
- Imaging scans:
  - Brain MRI – performed to assess eligibility

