Window(s):	$\leq 3$ weeks	$\leq 10$ days	$-\text{1/}$ $+2$ days	$-4$ days		$+14$ days	$+14$ days	every 6 months $\pm 30$ days for 10 years
	Section 2.3.2		Section 3.3.1					
Tumor biopsy (5.1.3)		X				X (optional)		

1. Performed within 10 years prior to treatment initiation
2. Performed within 4 weeks prior to treatment initiation
3. In participants with suspicion or prior history of treated CNS metastases only
4. Approximately 24-48 hours after the second dose of treatment
5. SG administration vital signs will include temperature, blood pressure, heart rate, and respiratory rate within 30 minutes prior to infusion, every 60 minutes during the infusion ( $\pm 10$  minutes), at end of infusion ( $\pm 10$  minutes), and 30 minutes post-infusion ( $\pm 10$  minutes)
6. For Cohorts 1 and 2 only.

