#### 6.3.3.2 Evaluation of Non-Target Lesions

**Complete Response (CR):** Disappearance of all non-target lesions and normalization of tumor marker level. All lymph nodes must be non-pathological in size (<10 mm short axis).

Note: If tumor markers are initially above the upper normal limit, they must normalize for a participant to be considered in complete clinical response.

**Non-CR/Non-PD:** Persistence of one or more non-target lesion(s) and/or maintenance of tumor marker level above the normal limits.

**Progressive Disease (PD):** Appearance of one or more new lesions and/or *unequivocal progression* of existing non-target lesions. *Unequivocal progression* should not normally trump target lesion status. It must be representative of overall disease status change, not a single lesion increase.

Although a clear progression of “non-target” lesions only is exceptional, the opinion of the treating physician should prevail in such circumstances, and the progression status should be confirmed at a later time by the review panel (or Principal Investigator).

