### 6.3.4 Duration of Response (DOR)

Duration of overall response: The duration of overall response is measured from the time measurement criteria are met for CR or PR (whichever is first recorded) until the first date that recurrent or progressive disease is objectively documented (taking as reference for progressive disease the smallest measurements recorded since the treatment started).

The duration of overall CR is measured from the time measurement criteria are first met for CR until the first date that progressive disease is objectively documented.

Duration of stable disease: Stable disease is measured from the start of the treatment until the criteria for progression are met, taking as reference the smallest measurements recorded since the treatment started, including the baseline measurements.

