### 10.4.2 Evaluable for objective response

Only those participants who have measurable disease present at baseline, have received at least one cycle of therapy, and have had their disease re-evaluated at the restaging scans will be

considered evaluable for response. These participants will have their response classified according to the definitions stated in Section [6.3](#). (Note: Participants who exhibit objective disease progression before their scheduled first restaging scans may be considered evaluable).

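### Does scheduling CA-125 only at baseline undermine response classification when complete response requires an elevated marker to normalise?

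*Combined protocol and SAP*

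**What the plan says.** Section 6.3.2 sets the marker condition: "If markers are initially above the upper normal limit, they must normalize for a participant to be considered in complete clinical response". Section 6.3.3.2 repeats it in the non-target criteria, where CR means "Disappearance of all non-target lesions and normalization of tumor marker level". The Non-CR/Non-PD category there includes "maintenance of tumor marker level above the normal limits".

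On collection, the laboratory list in section 3.3.2 names one tumor marker, CA-125. Section 3.3.1 leaves timing to the calendar: "Refer to Study Calendar (Section 3.4) for timing and applicable windows". The CA-125 row in section 3.4 has a single entry, at Baseline/C1D1, with the footnote "For Cohorts 1 and 2 only". The CBC row of the same table is marked across cycles and at end of treatment, so the blanks in the CA-125 row look intended.

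On use, section 10.4.2 applies the section 6.3 definitions to evaluable participants: "These participants will have their response classified according to the definitions stated in Section" 6.3. Section 10.5.2 defines ORR as the fraction with PR or CR, by cohort.

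**The concern.** The protocol measures the value that triggers the condition (raised at baseline) but never schedules the value that would satisfy it (normal later). Suppose a Cohort 1 participant has raised CA-125 at C1D1 and every lesion has gone at restaging. Section 6.3 asks whether the marker has normalised, and the scheduled data cannot answer.

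The text also has no explicit rule for a marker that was not measured. Non-CR/Non-PD describes a marker that stays high, and the best-overall-response table in section 6.3.3.3 has no marker column. One could fear that such a case would be scored CR by one reader and PR by another, or would turn on whether someone happened to order a test. At stake would be the CR count, best overall response, and the CR duration that section 6.3.4 defines: "The duration of overall CR is measured from the time measurement criteria are first met for CR".

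**Working it through.** **1. How the criteria treat the disputed case.** Take target lesions CR, non-target lesions gone, no new lesions, baseline CA-125 raised and no later value. Section 6.3.3.2 places the marker inside the non-target evaluation, so the table in section 6.3.3.3 can be read as follows:

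| Reading of the missing marker | Non-target status | Overall response |
|---|---|---|
| Normalisation not shown, treated as still raised | Non-CR/Non-PD | PR |
| Non-target component incomplete | Not evaluated | PR |
| Marker condition ignored | CR | CR |

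The first two readings give PR. The third sets aside an express requirement. No row turns the participant into stable disease or a non-responder. The evaluability rule in section 10.4.2 (measurable disease, one cycle, restaging) does not mention a marker, so nobody leaves the denominator either.

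**2. Effect on the primary endpoint.** Inputs from section 10.3 are p0 = 0.15, p1 = 0.35, stop at 0 or 1 of 10, and success at 6 or more of 22.

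The probability of success is the sum over x = 2 to 10 of P(X1 = x) × P(X2 ≥ 6 − x), with X1 ~ Bin(10, p) and X2 ~ Bin(12, p).

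- At p = 0.15: 0.0907, within the stated 10%.
- At p = 0.35: 0.804, meeting the stated 80%.
- Early stopping at p = 0.15: 0.544.

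The plan's design is reproduced. These figures depend only on the number of responders, CR + PR. With 6 responders of 22, every split from 0 CR/6 PR to 6 CR/0 PR gives ORR 6/22 = 27.3%, with a Clopper-Pearson 95% interval of 10.7% to 50.2%.

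**3. Effect on the secondary endpoints.** Overall duration of response (section 6.3.4) starts at the first CR or PR and ends at recurrence or progression judged on tumor measurements. PFS and OS (sections 6.3.5 and 6.3.6) do not use the CR/PR label. Section 10.5.3.2 lists duration of response, PFS and OS. It lists neither a CR rate nor CR duration.

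**4. How many participants.** Expected number = n × CR rate × share raised at baseline. The documents give neither rate for this population, so both are assumptions. The upper CR value of 7% is the rate quoted in section 1.2.3 for a different antibody-drug conjugate in cervical cancer. Section 1.2.4.2 describes the responses in the earlier endometrial series on this drug as PRs, so zero is plausible.

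- Cohorts 1 and 2 both full, n = 44: 44 × 0.07 × 1.00 = 3.08; 44 × 0.07 × 0.25 = 0.77; 44 × 0.05 × 0.50 = 1.10; 0% CR gives 0.
- At 5% and 50%, the chance of at least one case is 1 − (1 − 0.025)^44 = 0.67.
- Both cohorts stop at stage 1, n = 20: 20 × 0.07 × 1.00 = 1.40 at most.

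**The case for a change.** The best case for a change is that it would be cheap. Blood is already drawn on Day 1 of each cycle, so a repeat CA-125 in participants raised at baseline, plus a sentence on missing markers, would close the gap. Section 3.3.2 permits additional laboratory tests but does not require this one, so CR status could rest on discretionary testing. If a missing marker defaults to PR, nobody with raised baseline CA-125 could be called CR from scheduled data, which biases the CR count downward. Readers of a small single-arm trial will look at that count, and the protocol's own background reports CRs separately for other agents.

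Most of this stands as fact. The schedule and the definition do not match, and the entry in the table for unevaluated non-target lesions was not plainly written for markers. What does not stand is that the outcome is left open in a way that damages the results. Section 6.3.2 says the marker must normalise, so a CR without that evidence does not meet the definition. An investigator who wishes to assign CR can order the test when imaging first shows complete disappearance. The remaining bias runs in the conservative direction and touches a breakdown that section 10.5 does not list as an analysis.

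**Conclusion.** The observation is correct but calls for no change. It concerns only Cohort 1 and 2 participants with both raised baseline CA-125 and complete radiographic disappearance. Everyone else can be classified from scheduled data. For that overlap the text leans to PR, or to CR if an unscheduled CA-125 shows normalisation. Either way the participant is a responder, so the stage decisions, ORR and its interval, overall duration of response, PFS and OS are the same.

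The residual effect is a possible under-count of CRs: 0 to 3.1 of 44 on the assumed rates, with zero plausible. The documents do not allow a firmer figure. An analyst can handle this sensibly by scoring PR where normalisation is not documented and noting those cases beside the CR count. The conclusion rests on ORR remaining CR + PR pooled and on no CR-specific analysis being added to section 10.5.
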